7.3 Data and Safety Monitoring Board (DSMB)

We will utilize the NC TraCS DSMB for additional regulatory monitoring of the study. The DSMB will review aggregate safety data after enrollment of 25, 50, and 75% of the study participants. There will be several criteria for evaluating safety and possible early stopping of the trial. Adverse events will be graded based on the CTCAE criteria listed above (7.2 AE Reporting).

- 1) Pneumothorax – If 2 out of 10, or if more than 10 enrolled, 20% out of enrolled subjects experience pneumothorax, then the study will be suspended until the DSMB can review the information and provide recommendations.
- 2) Hypotension – If 2 out of 10, or if more than 10 enrolled, 20% out of enrolled subjects experience refractory hypotension, then the study will be suspended until the DSMB can review the information and provide recommendations.
- 3) Death – If 8 out of 10, or if more than 10 enrolled, 60% out of enrolled subjects die, then the study will be suspended until the DSMB can review the information and provide recommendations.

There are no stopping rules for efficacy, as there will be no interim efficacy analyses. The study is only adequately powered to detect an efficacy difference if it were completed.

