Safety Evaluations	Periodic review will be performed by the NC TraCS DSMB. They will review aggregate safety data after 25, 50, and 75% enrollment to ensure there are not safety differences between the groups in hypotension requiring vasopressors and development of pneumothorax. All patients will have

continuous monitoring of HR, BP, and oxygenation per ICU protocol to monitor patient safety.

Statistical And Analytic Plan

This is a randomized, controlled trial to evaluate the effect of using Optimal PEEP based on an esophageal balloon measurement on duration of mechanical ventilation. We hypothesize that using Ptp to identify optimal PEEP will reduce time on the ventilator and therefore increase the ventilator free days at day 28. The primary outcome is the number of ventilator-free days, defined as the number of days alive and ventilator-free by day 28. Differences between the two groups in the primary outcome will be analyzed using independent t-tests and a linear regression model adjusting for BMI, abdominal girth, and Ptp.

DATA AND SAFETY MONITORING PLAN

The PI will be responsible for maintaining patient data and ensuring accuracy of the data collected. All patient data will be collected using REDCap through the NC TraCS system. REDCap allows for immediate data validation and range setting to reduce the likelihood of erroneous data entry. Data created for analysis will be de-identified and secured on a password protected UNC School of Medicine network hard drive. All investigators will be trained on completing the electronic case report form.

Patient safety will be monitored with continuous cardiovascular monitoring by the critical care team. Subject stopping rules will be in place to end the study intervention, including refractory hypotension, development of pneumothorax, or changes in oxygenation or hemodynamics that the primary team feels may be related to changes in PEEP.

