7.2 Data and Safety Monitoring Plan

All participants will be continuously monitored by critical care nurses under the guidance of critical care physicians per individual ICU protocols.

Stopping rules and procedures

Subject stopping rules will be the development of any of the following after randomization:

- New pneumothorax
 - Pneumothorax is a known risk factor for all patients requiring mechanical ventilation with a case rate of <1% of all mechanically ventilated patients. In previous studies of optimal PEEP determination using esophageal balloon-guided pressure measurement, no pneumothoraces were observed. We believe the study procedures will be safe for both arms, and that the intervention arm will be at lower risk for this outcome. However, development of a pneumothorax will necessitate a chest tube and will invalidate the measurement of pleural pressure. Therefore the study procedures must be stopped.
- Epistaxis requiring intervention
 - In the event of epistaxis requiring packing or intervention, the esophageal balloon will be removed and the study subject's participation in the study will end.
- Hypotension
 - In the event a patient experiences a drop in mean arterial pressure (MAP) below 65 mm Hg or a significant change in vasoactive medication requirement (>10 mcg/min dose of norepinephrine equivalent), that is felt by the clinical ICU team to possibly be related to the intervention, the study subject's PEEP will be dropped by 2 cm H₂O every 5 minutes until the parameter returns to an acceptable range (as determined by the clinical ICU team) or until the PEEP reaches the pre-intervention level. The patient will remain on no higher than this new PEEP for the remainder of the study.

Adverse Event Reporting

All Adverse Events will be documented and graded using CTCAE grading, defined as any patient who develops one of the following (by CTCAE grading):

- grade 3-5 hypotension
- grade 2-5 pneumothorax
- grade 2-5 epistaxis

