Screening for possible adverse events will occur daily. Each possible adverse event will be reviewed by a UNC critical care physician, independent of the study, within 72 hours of occurrence. The primary independent reviewer will be [name], MSCR; if he is on clinical service responsible for the study subject, then [name], PhD will serve as the independent reviewer. After independent review, events considered to be probably or definitely related to the intervention will be submitted to the IRB for review. In addition, we will utilize a Data and Safety Monitoring Board to review aggregate safety data.

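### The death suspension trigger needs 8 deaths at 10 enrolled but only 7 at 11, so enrolling a patient with no event can suspend the study

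*Combined protocol and SAP*

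**What the plan says.** Section 7.3 (Data and Safety Monitoring Board) sets three numerical triggers.

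- **Death:** "If 8 out of 10, or if more than 10 enrolled, 60% out of enrolled subjects die".
- **Pneumothorax:** "If 2 out of 10, or if more than 10 enrolled, 20% out of enrolled subjects experience pneumothorax".
- **Hypotension:** the same numbers as pneumothorax, applied to refractory hypotension.

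The consequence is the same for each: "then the study will be suspended until the DSMB can review the information and provide recommendations". It is a pause, not termination.

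Separately from the triggers, "The DSMB will review aggregate safety data after enrollment of 25, 50, and 75% of the study participants". Section 7.2 adds that "Screening for possible adverse events will occur daily", with independent review of each possible event within 72 hours. The plan gives no expected mortality, no derivation of the death trigger and no operating characteristics for it.

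**The concern.** Each trigger has one clause for the first ten patients and another for later enrolment. For pneumothorax and hypotension the clauses agree where they meet, because 2 of 10 is 20%. For death they do not: 8 of 10 is 80%, and the next clause is 60%.

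A more demanding percentage at small numbers can be a deliberate choice. The difficulty is that the drop from 80% to 60% is large enough to lower the number of deaths required, not just the percentage. An additional patient with no event is reassuring if it is evidence of anything. Under the written rule, that patient can turn a position that does not suspend the study into one that does. Whoever applies the rule around the tenth and eleventh enrolment would have to suspend with no new death, or query the text with the DSMB at that moment.

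**Working it through.** **Inputs from the documents.** The death trigger is 8 of 10, then 60% of enrolled above 10 (section 7.3). The pneumothorax and hypotension triggers are 2 of 10, then 20% of enrolled above 10 (section 7.3). Total enrolment is 76 (section 6.3).

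**Assumptions.** The first clause is read as 8 (or 2) events among up to 10 enrolled. Mortality is assumed to be 30%, 40% or 50%, because the documents give none. For the probabilities only, each patient's outcome is taken as known at enrolment. The required counts do not depend on mortality or on this simplification.

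**Step 1. Deaths required.** Above 10 enrolled, this is the smallest whole number k with k/n of at least 0.60.

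| Enrolled n | 0.60 × n | Deaths required | Do 7 deaths suspend? |
|---|---|---|---|
| 10 | first clause applies | 8 (80%) | No (70.0%) |
| 11 | 6.6 | 7 | Yes (63.6%) |
| 12 | 7.2 | 8 | No (58.3%) |
| 13 | 7.8 | 8 | No (53.8%) |
| 14 | 8.4 | 9 | No (50.0%) |

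Reading the second clause as strictly more than 60% also gives 7 at n = 11. Over every n from 1 to 76, the step from 10 to 11 is the only fall.

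**Step 2. The other triggers.** At n = 10 the count is 2. At n = 11, 0.20 × 11 = 2.2, so the count is 3. It never falls between 1 and 76.

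**Step 3. How often the anomalous path occurs.** P(exactly 7 deaths in 10) × P(no death in the 11th) = C(10,7) p⁷(1−p)³ × (1−p), where C(10,7) = 120.

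- p = 0.30: 0.0090 × 0.70 = 0.6%
- p = 0.40: 0.0425 × 0.60 = 2.5%
- p = 0.50: 0.1172 × 0.50 = 5.9%

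**Step 4. Does the anomaly change which trials are suspended?** Compare the written rule with one that requires the larger of 7 deaths and 60% of enrolled. That rule needs 7 deaths at every n from 7 to 11 and matches the written rule from n = 11 on.

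- If it fires by n = 10, there are at least 7 deaths, so at n = 11 there are at least 7 of 11 and the written rule has fired too.
- In the other direction, 8 deaths among the first ten exceeds 7, so the floor-7 rule has also fired.

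The two rules suspend the same trials. The longest delay is when the first seven patients all die and the next four do not: n = 7 against n = 11, which is 4 enrolments. In 200,000 simulated trials at each assumed mortality, none differed in whether it was suspended.

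**Step 5. Chance that the trigger ever fires in 76 patients** (exact patient-by-patient recursion).

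| Rule | 30% | 40% | 50% |
|---|---|---|---|
| As written | 3.2% | 15.9% | 47.3% |
| 60%, floor of 7 deaths | 3.2% | 15.9% | 47.3% |
| 60%, floor of 8 deaths | 2.4% | 14.0% | 45.2% |
| 60%, floor of 6 deaths | 5.4% | 20.7% | 51.9% |

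None of the three alternatives has a required count that falls as enrolment rises.

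**The case against.** The strongest reply has three parts.

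*The clauses do not contradict each other.* They cover different enrolment counts, and each count has exactly one answer. This stands. The defect is that the required count falls, not that one situation receives two answers. The documents also cannot show what the authors intended, and the point does not rest on intent.

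*The consequence is slight.* This also stands. A reader might divide the path probabilities in step 3 by the firing rates in step 5 and infer that 12% to 20% of suspensions would be mistaken. The documents do not support that. Step 4 shows that a rule without the fall, with a floor of 7, suspends exactly the same trials, so against it the written rule only delays suspension.

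*The probabilities rest on assumptions.* Mortality is assumed, and so is knowing each outcome at enrolment. With 3–4 enrolments a month and 28-day participation (section 3.3), deaths among the first ten may be recorded only after the eleventh patient has joined. An eleventh patient also has no event on the day of enrolment, whatever happens later. Counting on that basis, the relevant figure is P(exactly 7 of 10): 0.9%, 4.2% or 11.7% in place of 0.6%, 2.5% or 5.9%. This stands as a caution on frequency. It does not touch the required counts.

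A reader might also infer that the pooled 20% pneumothorax trigger is an error, because section 7.2 cites a "case rate of <1% of all mechanically ventilated patients". The documents do not support that either. The synopsis says the scheduled DSMB reviews are to "ensure there are not safety differences between the groups in hypotension requiring vasopressors and development of pneumothorax", and section 7.2 provides daily screening and independent review of each event. The trigger is a backstop beside these. A more sensitive one would bring more pauses when the arms carry equal risk, so its level is a judgement for the DSMB.

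**Conclusion.** The point holds and is minor. The death trigger in section 7.3 is wrong as written at one step: the required number of deaths is 8 at 10 enrolled, 7 at 11 and 8 at 12. This follows from the plan's own numbers and needs no assumed rate.

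The practical effect is small. It arises only with exactly 7 deaths at the step from 10 to 11, and it leads to a pause for DSMB review. The frequencies quoted depend on assumed mortality of 30% to 50% and on outcomes being known at enrolment. The finding does not show that the trial would be wrongly suspended or wrongly continued, or that the pneumothorax and hypotension triggers are defective.

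**What to change.** The sponsor and DSMB should reconcile the 8-of-10 clause with the 60% clause in section 7.3 so that the number of deaths required never falls as enrolment rises. One sentence giving a percentage together with a minimum number of deaths would do it. Which threshold and which minimum to use is their decision.

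The cost is wording only. Of the examples in step 5, a floor of 7 leaves the chance of ever firing unchanged at each assumed mortality. A floor of 8 lowers it by about 1 to 2 percentage points, and a floor of 6 raises it by about 2 to 5. Sample size, the schedule of DSMB reviews and the other two triggers are unaffected.

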8 DATA COLLECTION AND MANAGEMENT

All patient data will be collected using UNC REDCap through the NC TraCS system. REDCap allows for immediate data validation and range setting to reduce the likelihood of erroneous data entry. Data created for analysis will be de-identified and secured on a password protected UNC School of Medicine network hard drive. All investigators will be trained on completing the electronic case report form.

All data will be recorded on computerized case report forms via REDCap, which will be transferred (after de-identification, as follows) to a centralized database constructed and operated for this project by the UNC TraCS Clinical Research Data Management Service. This database system provides for secure web-based data entry with the data stored on servers that we maintain. The data is encrypted during transmission. The servers are located in a secure campus area with all the appropriate physical security measures in place. One ITS group manages the space where the servers are housed, but that

team does not have access or manage content on the servers. UNC-Chapel Hill's TraCS IT staff (a team of 5 and the research team will have access to data collected in this study, as standard for most University server spaces. Research teams are provided access at the user level, per site. Only the investigators and project manager will have access to aggregate data. The data is encrypted during transmission using industry standards of TSL 1.1 algorithms (including MD5, AES, etc). The web and database servers are monitored by the TraCS IT staff, patched frequently, and scanned by a third party vendor to ensure that they are protected against known vulnerabilities. The scanning application is the standard service for the entire campus. Access is by individual user id with User-level permissions that define only those records an individual is authorized to see and is restricted to the forms and/or functions that the user needs to have. The applications themselves are written using open source tools, and have also been scanned by campus security office to ensure that the applications also are protected from known exploits. The data is backed up to electronic media on a daily basis. The electronic media is secured by ITS stored in a secure area separate from the servers.

The UNC TraCS Clinical Research Data Management Service endeavors to preserve the privacy, confidentiality, and security of protected health information that may be part of health records or research datasets. Protected Health Information (PHI) is handled according to appropriate Health Insurance Portability and Accountability Act of 1996 (HIPAA) Privacy and Security Regulations. Staff who work with PHI are required to complete appropriate HIPAA and other compliance training in accordance with institution policy.

9 RECRUITMENT STRATEGY

Potential participants will be identified from daily screening of intubated patients in the MICU of each study site by research personnel. After identification of potential participants, study team members will approach the critical care team for confirmation of appropriateness and permission to enroll participants. If the clinician is agreeable, a study team member will approach the legally authorized representative for explanation of the study.

The patients' decision-making surrogates will be primarily approached to consent for participation in this study as most mechanically ventilated patients are medically or clinically sedated and not able to have decision making capacity. The investigators and/or research coordinators will approach the surrogates individually after the patients are identified as being eligible for the study to provide an informed consent process. Full disclosure will be provided that enrollment in this study will be optional and not affect major treatment decisions.

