3 INVESTIGATIONAL PLAN

3.1 Study Design

We will conduct an open label randomized controlled clinical trial to evaluate the impact of titration to Optimal PEEP compared to use of a standardized PEEP table on the duration of mechanical ventilation in obese patients with acute respiratory failure. Patients will be followed for 28 days to evaluate for ventilator-free days. Blinding of the clinical team will not be possible due to the differences in treatment approach, including the performance of spontaneous breathing trials.

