5 STUDY EVALUATIONS AND MEASUREMENTS

5.1 Measurements

Procedures for PEEP and FiO2 Titration

Both groups will have their FiO2 titrated based on results of the PaO2 from an arterial blood gas, if available, or SpO2 values if no arterial blood gas is obtained. PEEP titration will vary by group as below.

Setting PEEP in Intervention Group

The waveforms of Paw, Pes, and Ptp will be visualized on the ventilator. Ptp is obtained from Paw – Pes. PEEP will be increased on the ventilator to achieve a Ptp between 0 and +2 cm H₂O (Optimal PEEP). Measurements will be obtained daily and adjustments to PEEP will occur daily. PEEP will be reduced below Optimal PEEP in the setting of hemodynamic compromise (requiring increasing vasoactive medications for blood pressure support).

Setting PEEP in Control Group

PEEP in the control group will be determined by High PEEP ARDSnet PEEP/FiO₂ table. Titration of PEEP will occur when clinically indicated by PaO₂ or SpO₂, and FiO₂. We chose the High PEEP table based on the clinical suspicion that obese patients may require higher PEEP levels on average than non-obese patients to balance the additional pressure of their chest wall. In addition, EPVent2, a study of esophageal balloon PEEP titration in patients with ARDS utilized the High PEEP table. Patients with moderate and severe ARDS benefit from higher levels of PEEP. (8)

Procedures for Assessment of Readiness for Extubation

Both groups will have a daily assessment of readiness for extubation performed by the Respiratory Therapist and bedside RN according to the standard clinical protocol. Criteria for both groups to undergo a spontaneous breathing trial (SBT) will be the following:

- 1) Not in prone position
- 2) No increased ICP
- 3) No active seizures
- 4) No alcohol withdrawal requiring escalating treatment
- 5) No active myocardial ischemia in discussion with nursing or physician
- 6) No unstable spine fractures
- 7) No free muscle flaps
- 8) FiO₂ ≤ 50% and SpO₂ ≥ 90%
- 9) Minute Ventilation < 15 L/min
- 10) Minimal vasopressors (norepinephrine < 5mcg/min or 0.05 mcg/kg/min, dopamine/dobutamine ≤ 5 mcg/kg/min)
- 11) HR < 140
- 12) RR ≤ 35
- 13) SBP > 90 and < 180

Failure of an SBT will be demonstrated if any of the following criteria are met:

- 1) SpO₂ < 90% sustained ≥ 5 minutes
- 2) Spontaneous VT ≤ 4ml/kg IBW – sustained ≥ 5 minutes
- 3) Respiratory Rate ≥ 35/min
- 4) Rapid Shallow Breathing Index >105

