- 5) Other signs of respiratory distress (distress = 2 or more)
- 6) HR > 140
- 7) Marked accessory muscle use
- 8) Abdominal paradox (belly breathing)
- 9) Diaphoresis

Failure of an SBT will be determined by the bedside RT based on current policy (PolicyStat ID: 4745433). If a patient fails an SBT, they will be returned to their previous ventilator settings until the next daily assessment. If the patient tolerates a 30-minute SBT, they will be returned to their previous ventilator settings for 60 minutes, then extubated to an appropriate oxygen delivery device. Ventilator settings during the SBT and extubation procedures will vary between groups as below. Blinding of the respiratory therapist determining eligibility for SBT to treatment arm will not be possible because of the differences between SBT protocols. However, the study team will make no determinations of readiness for extubation. If a member of the study team is on service during the time of potential enrollment, these patients will be excluded to avoid bias.

SBT and Extubation Procedure for Intervention Group

Patients in the Intervention group will undergo an SBT regardless of their PEEP level. The PEEP that generates a Ptp of 0 will be considered their optimal PEEP, and this will not be lowered for the SBT. The Intervention Group SBT will consist of a trial of a pressure support of 5 cm H₂O and Optimal PEEP.

SBT and Extubation Procedure for Control Group

Patients in the Control group will undergo an SBT **when they reach a PEEP \leq 8 cm H₂O**. This is the current standard of care based on the SBT protocol at UNC Hospitals. SBT and extubation prior to meeting these criteria will be based on primary medical team's discretion and will be recorded for analysis and safety tracking.

Procedures for ventilator weaning after tracheostomy

Any patient who fails to be eligible for extubation or fails extubation will be eligible for tracheostomy per usual unit protocol. The study team will play no part in the decision to proceed with tracheostomy for ventilator weaning. After tracheostomy, it is routine practice to forego SBT and proceed with trials of liberation from the ventilator with oxygen delivered by an aerosol tracheostomy collar ("trach collar trials" or TCT). The same criteria are used to perform a TCT as an SBT above. The two groups will have different approaches to TCT.

TCT Procedure common to both groups

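### The Section 9 disclosure that enrolment will not affect major treatment decisions conflicts, on its natural reading, with the ventilator management that Sections 4.3 and 5.1 tie to enrolment and allocation

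*Combined protocol and SAP*

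**What the plan says.** Section 9 (Recruitment Strategy) describes the approach to surrogates, who will give most of the consent because most ventilated patients lack capacity. It ends: "Full disclosure will be provided that enrollment in this study will be optional and not affect major treatment decisions".

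Other sections describe what enrolment and allocation change:

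- **Balloon.** Section 4.3 has a research investigator place an esophageal balloon catheter in every patient in both groups. Section 7.1 describes its risks as relatively small and lists them.
- **PEEP.** Section 5.1 states that "PEEP titration will vary by group as below". The intervention arm is titrated to a transpulmonary pressure target. For controls, "PEEP in the control group will be determined by High PEEP ARDSnet PEEP/FiO₂ table". The study team selected that table: "We chose the High PEEP table based on the clinical suspicion" that obese patients may need higher PEEP.
- **Breathing trials and extubation.** Section 5.1 says "Ventilator settings during the SBT and extubation procedures will vary between groups as below". "Patients in the Intervention group will undergo an SBT regardless of their PEEP level", whereas controls have an SBT once PEEP is 8 cm H₂O or lower.
- **Trach-collar trials.** Section 5.1 requires a speaking valve in the intervention arm and leaves it optional in the control arm.

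Section 3.1 explains that the clinical team cannot be blinded "due to the differences in treatment approach, including the performance of spontaneous breathing trials".

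Section 10 adds a different assurance, that refusing to take part does not jeopardize care. It also says that study information and an IRB-approved consent form will be reviewed with the next of kin.

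**The concern.** The sentence in Section 9 is presented as disclosure, so it should match what the protocol does. A surrogate who hears that enrolment leaves major treatment decisions untouched could reasonably take this to cover how the ventilator is set and when its removal is tried. The trial randomizes the first of these and the conditions for the second. Its primary objective (Section 2.1) is to shorten ventilation by doing so.

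What is at stake is mainly the accuracy of what surrogates are told. Most participants cannot speak for themselves, and Section 10 relies on an appropriately informed representative. A protocol that states two different things also leaves site staff unsure which to say.

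A secondary matter concerns the data. Section 10 plans reconsent for patients who recover cognition during the hospitalization. Withdrawal of consent ends participation (Section 4.4), and missing values are to be ignored (Section 6.2). Any loss at reconsent would come only from patients who are alive and recovered, so it would be related to ventilator-free days.

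**Working it through.** The plan gives no figure on this point. The check compares the Section 9 statement with each procedure, and then counts columns in the protocol's own PEEP table.

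**Step 1. Does enrolment or allocation change the element?**

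| Element | Intervention arm | Control arm | Changed by |
|---|---|---|---|
| Esophageal balloon (4.3) | Placed | Placed | Enrolment |
| Method of setting PEEP (5.1) | Transpulmonary pressure target | High PEEP table | Allocation |
| PEEP condition for an SBT (5.1) | None | 8 cm H₂O or lower, with team discretion | Allocation |
| Ventilator settings during the SBT (5.1) | Pressure support of 5 cm H₂O at Optimal PEEP | Said to differ; not spelled out | Allocation |
| Speaking valve in trach-collar trials (5.1) | Required | Optional | Allocation |
| Readiness for extubation (5.1) | Not decided by study team | Not decided by study team | Neither |
| Decision for tracheostomy (5.1) | Not decided by study team | Not decided by study team | Neither |

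Five of the seven elements depend on enrolment or allocation. Two are kept outside the study team.

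**Step 2. Is the SBT difference material?** Section 5.1 links the SBT to extubation: a patient who tolerates 30 minutes goes back to the previous settings for 60 minutes and is then extubated. The size of the difference can be read from inputs in the protocol:

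- The SBT criteria common to both arms (5.1) allow FiO₂ of 50% or less.
- In the Higher PEEP table (Appendix 12.1), the columns that include FiO₂ of 0.5 or less are five at 0.3, two at 0.4, two at 0.5 and one at 0.5–0.8: 5 + 2 + 2 + 1 = 10.
- Of these 10, the columns with PEEP of 8 or lower are PEEP 5 and PEEP 8, both at FiO₂ 0.3: 2.

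So 2 of the 10 table settings compatible with the shared FiO₂ criterion also meet the control arm's PEEP condition. The intervention arm has no PEEP condition. This counts table columns, not patients, and it leaves aside the primary team's discretion. It shows that allocation materially changes when an SBT, and so extubation, becomes available under the protocol. It says nothing about which rule is clinically right.

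**Step 3. Does another passage remove the conflict?** Section 10's assurance concerns refusal. Section 9's sentence concerns enrolment. One can be true while the other is not, so Section 10 does not cure Section 9.

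**Step 4. Does it affect the statistics?** The sample size, alpha, power and primary test do not depend on the Section 9 wording. The only route to the data is withdrawal, through Sections 4.4 and 6.2, and the documents give no rate for it.

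**The case against.** The strongest reply is that major treatment decisions is undefined and can be read narrowly. The study team makes no determination of extubation readiness and takes no part in the tracheostomy decision. Readiness is assessed daily by the respiratory therapist and bedside nurse under the standard clinical protocol, with criteria common to both arms. The primary team must agree before the family is approached (Sections 4.1 and 9) and can end participation (Section 4.4). In controls, the PEEP condition is described as current standard of care at UNC Hospitals, and "SBT and extubation prior to meeting these criteria will be based on primary medical team's discretion".

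Much of this stands. On the narrow reading the sentence is loose rather than flatly false, and the control-arm SBT condition is not a fixed bar. But the standard-of-care description names UNC only, while Vidant also enrols (Section 3.4). It does not cover the intervention-arm rules, the study's choice of the High PEEP table for controls, or the balloon. The literal reading remains the more natural one.

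A reader might also infer that consent rests on a false statement, or that patients were promised their ventilator management would not change. The documents do not support this. Section 10 provides for a consent form and a review of study information. The form is not among the documents, and it may well be accurate.

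A reader might further infer that this sentence will cause withdrawals that use up the dropout allowance (76 − 68 = 8 patients). Nothing in the documents links the sentence to withdrawals, and reconsent carries that risk however Section 9 is worded. The figure of 8 does not measure any effect of this sentence.

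**Conclusion.** The point holds as an internal inconsistency in planned disclosure. On its natural reading, the Section 9 sentence conflicts with Sections 4.3 and 5.1, and with Section 3.1's own account of why the clinical team cannot be blinded. It could bear on the consent for all 76 planned participants, most of it given by surrogates.

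The conclusion assumes that an ordinary listener would count the setting of PEEP and the conditions for trying extubation as major treatment decisions. It does not extend to the validity of consent or the content of the consent form. It does not change the sample size, error rates or analysis.

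The follow-up issue is separate and secondary. Loss at reconsent would be outcome-related if it occurred, but its frequency cannot be estimated from the documents.

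**What to change.** Reconcile the Section 9 sentence with Sections 4.3 and 5.1. The replacement should say that:

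- enrolment is optional, and declining does not affect care;
- enrolment assigns by chance the method of setting PEEP and the breathing-trial and trach-collar procedures;
- the clinical team keeps the decisions that the protocol leaves to it, namely extubation readiness, tracheostomy, and early SBT or extubation in controls;
- both arms receive an esophageal balloon for research.

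Check the consent form and any recruitment script for the same phrase, and correct it there if it appears.

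Separately, ask at reconsent or withdrawal for permission to keep collecting ventilator and survival status to day 28 after study procedures stop. This protects the primary outcome whatever Section 9 says.

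The cost is an IRB wording amendment and possibly a slightly lower consent rate. No clinical rule, sample size or analysis changes.
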